PE	Physical Exam
PET/CT	Positron Emissions Tomography / Computed Tomography
PIV	Prescription Isodose Volume
PIV/TV	Prescription Isodose Volume/Tumor Volume
PMD	Progressive Metabolic Disease
PMR	Partial Metabolic Response
PO	By mouth
PR	Partial Response
PTV	Planning Target Volume
QOL	Quality of Life
RECIST	Response Evaluation Criteria in Solid Tumors
RPM	Real-time Position Management
RT	Radiation Therapy
RTOG	Radiation Therapy Oncology Group
SD	Stable Disease
SBRT	Stereotactic Body Radiotherapy
SMA	Superior Mesenteric Artery
SMD	Stable Metabolic Disease
SMS	Short Metal Stent
SMV/PV	Superior Mesenteric Vein / Portal Vein
SUV	Standard Uptake Value
TPP	Time to Progression
TV	Tumor Volume
WOOCBP	Women of Child-Bearing Potential

PROTOCOL SUMMARY

Title

Pre-operative Stereotactic Radiosurgery Followed by Resection for Brain Metastases
Phase II Study Determining the Efficacy of Pre-operative Stereotactic Radiosurgery
Followed by Resection for Brain Metastases

Objectives

The *primary* objective of this study is to determine the efficacy of giving pre-operative radiosurgery to patients pending resection of a brain metastasis.

The *secondary* objectives of this study are:

1. To evaluate overall survival (OS)
2. To evaluate distant intracranial failure associated with this therapy.
3. To evaluate the Health Related Quality of Life (HRQL) associated with this therapy.

The *exploratory* objectives of this study are:

1. To collect and store the resected body tissue(s) and blood samples for potential correlation to clinical outcome.

Patient population

In order to be eligible for this study, patients must have an extra-cranial primary tumor diagnosis and no more than 4 distinct lesions within the brain. Patients must be at least 18 years of age and able to give informed consent. They must have a Karnofsky Performance Status ≥ 50 and a life expectancy of at least 12 weeks.

Number of patients

24

Study design and methodology

This is a prospective single-arm phase II study. The treatment schema detail is in Section 6.3.

Treatment administered

Patients will receive a single fraction pre-operative stereotactic radiosurgery radiation dose. The dose will be determined by the diameter of the tumor.

Efficacy data collected

The following evaluations will be performed to assess the efficacy of preoperative stereotactic radiation therapy:

- Objective local control rate measuring tumor volume
- Health Related Quality of Life assessment using the Functional Assessment of Cancer Therapy – Brain (FACT-Br) tool.

Safety data collected

The following evaluations will be conducted to assess the safety of radiosurgery:

- Recording of all toxicity data per NCI CTCAE version 4.0

1.0 BACKGROUND

1.1 Brain metastases and whole brain radiation therapy

Brain metastases are a frequent cause of morbidity and mortality representing the most common intracranial tumor in adults, affecting upwards of 30-40% of all cancer patients [1-3]. There exist multiple treatment options for patients with brain metastases including: whole brain radiation therapy (WBRT), surgical resection, and stereotactic radiosurgery (SRS) [4-9]. Without treatment the prognosis is often poor, with survival limited to only a few months [10].

The mainstay of treatment for brain metastases has been WBRT, which has been used for decades and is thus well studied. The use of WBRT for patients with brain metastases from various primary cancers has been shown to improve both existing neurologic symptoms and overall survival compared to corticosteroids and supportive care (median survival = 4-5 months) [11]. Unfortunately, the use of WBRT is associated with neurotoxicity and neurocognitive decline, especially in long-term survivors [12].

Surgical resection has been typically reserved for patients with good performance status, limited intracranial disease, isolated symptomatic lesions, and lesions resistant to WBRT [13, 14]. For patients with a solitary accessible lesion, surgical resection has been shown to be an effective primary treatment approach that is able to relieve mass effect and improve survival [14]. However, the limitation of surgical resection alone as a treatment modality is associated with high rates of local failure [8]. Interestingly, the benefit of WBRT as an adjuvant treatment post-surgical resection has been established. WBRT alone has been compared to surgery followed by WBRT and several studies have shown both improved local control (LC) and reduced neurological death with the latter approach [15-17].

1.2 Sterotactic radiation surgery (SRS)

In more recent years, SRS has been shown to be an effective alternative therapy for patients with brain metastases. It is especially useful in patients with progression of disease following WBRT, for whom treatment-related neurotoxicity is a major concern. SRS enables the delivery of a highly focused radiation dose to a small target with rapid fall-off, thereby limiting radiation to the surrounding normal brain tissue. This feature should potentially reduce the likelihood of developing late neurocognitive deficits, an issue that becomes an increasing concern in long-term survivors. SRS has even emerged as a treatment strategy to limit WBRT and has been studied in the setting of brain metastasis. SRS has been investigated in postoperative management of solitary brain metastases. At least a dozen retrospective reports have been published describing the results of adjuvant SRS. The reported 1-year local control rates is variable and has been found to be as low as 35% and as high as 100% [18, 19]. Review of UPMC's institutional experience showed 6-month and 1-year LC of 76% and 76% respectively, which is consistent with most other reports [20].

However, delivery of postoperative SRS is particularly challenging due to the nebulous appearance of the tumor bed after resection. This difficulty of delineating the margins of the resection cavity may be responsible for the rate of local failure (LF) despite the utilization of adjuvant therapy and lead to additional symptomatic brain necrosis. A commonly employed strategy to improve LC with adjuvant SRS is the addition of a margin to account for target uncertainty and microscopic extension of disease. The Stanford University group reported a significant improvement in (LF) rates with the addition of a 2-mm margin (1-year LF: 3% vs. 16%) without an associated increase in toxicity [21]. In contrast, a French group has reported an experience of delivering SRS with a 2-mm margin and reported no improvement in 1-year LC (69% vs. 72%) and an increased rate of severe parenchymal complications [22].

In addition to localizing the tumor bed, another potential negative consequence to the sequence of postoperative SRS is the time course between resection and radiation treatment. Typically SRS is performed several weeks after surgical removal of brain metastases. During this interval, the tumor bed is given additional time and may have a detrimental impact on LC.

For these reasons, once a patient has been deemed a candidate for surgical resection of a brain metastasis, it is generally accepted that radiation of some form must be given to facilitate local control. For patients with a symptomatic or sizable brain metastasis that requires surgical resection, one option is to perform radiosurgery up front, followed by surgical removal of the tumor.

1.3 Pre-operative SRS

For patients who require surgical removal of a brain metastasis, we hypothesize a more sensible strategy to improve LC may be the delivery of pre-operative SRS followed by immediate tumor resection. Pre-operative target delineation is likely to be more accurate and result in fewer marginal misses. Furthermore, this treatment package could be completed more expeditiously by eliminating the prolonged interval from surgery to SRS. In our experience, this interval was approximately 5 weeks. In addition, the same MRI scan could be used for SRS and surgical resection; resulting in cost savings for patients who otherwise would receive two separate MRI scans for treatment. Finally, pre-operative SRS may facilitate better resection margins by the delivery of dose in the radiation penumbra surrounding the tumor. An early study of pre-operative SRS on brain metastases by Stuart Burri et al., 2010 demonstrated actuarial LC of 97.7%, 84.6%, and 64.0% at six, twelve, and twenty four months, respectively [23]. More recently according to the interim analysis from a phase 1 study of pre-operative SRS for brain metastases by the University of Alabama, pre-operative SRS appears safe with low rates of wound complications or acute grade toxicity along with target volume reduction of 39% [24]. We therefore propose a phase II clinical trial to further investigate the efficacy of this novel approach.

2.0 OBJECTIVES

Primary

- 2.1 To determine the efficacy of giving pre-operative radiosurgery to patients pending resection of a brain metastasis. The primary outcome will be measured by local control rate; that is, the tumor volume as measured at a later date and compared to the tumor volume at the start of radiotherapy (time frame: up to 3 years).

Secondary

The secondary objectives of this study are:

- 2.2 To determine the overall survival (OS) as measured by the length of time after the beginning of treatment that diagnosed patient remains alive.
- 2.3 To evaluate distant intracranial failure associated with this therapy as measured by the presence of new brain metastases identified via magnetic resonance image. The imaging will be conducted every 3 months for 12 months, then every 4 months for up to 3 years.
- 2.4 To measure Health Related Quality of Life (HRQL) in patients with primary brain tumors treated with stereotactic radiosurgery using the Functional Assessment of Cancer Therapy-Brain assessment tool for up to 3 years.

The exploratory objective of this study is:

To collect and store the resected body tissue(s) and blood samples for potential correlation to clinical outcome.

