3.5 Timeline of study procedures

Once eligible by screening, stereotactic radiosurgery will take place, 1-7 days later, there will be a surgical removal of the tumor. Monitoring will take place 10-14 days after surgery, every 3 months for the first year and every 4 months thereafter.

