3.6.2 Evaluation during treatment

Administration of stereotactic radio surgery:

Patients will receive a single fraction pre-operative SRS radiation dose. The dose will be determined depending on diameter of the tumor as follows: 24 Gy, 18 Gy, and 15 Gy for tumors < 21 mm, 21-30 mm, and 31-40 mm in maximum diameter respectively.

Dose	Diameter
15 Gy	31-40 mm
18 Gy	21-30 mm
24 Gy	< 21mm

Tumor tissue collection only if participant agrees and there is leftover from clinical collection.

Blood sample collection pre and post SRS treatment (within 24 hours)

Complete physical evaluation with a performance status, vital signs, height, and weight, and a complete medical history

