3.7 Surgical removal

One to seven days after the single SRS, patient will then be prepared for surgical removal of the tumor that was designated by surgeon as part of normal standard of care for dominant brain metastasis. Only the symptomatic tumor will be removed surgically. Surgery will be performed at Shadyside Hospital.

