4.2.2 Justification of sample size/accrual rate

No more than 24 evaluable patients will be treated in the trial. This study of 24 patients will have 80% power to detect a difference in postulated local tumor control of 85% to a known inference local tumor control set at 60% to be excluded, using a 1-sided test with Type I error rate of 0.05 for 6, 12, and 24 months. The sample size was estimated using a non-inferior power analysis for inference of a single proportion compared to a known proportion. Also, an attrition rate of 20% was included into the estimated sample size. Based on previous efforts in recruiting patients at the University of Pittsburgh Cancer Institute, it is anticipated that at least 5 patients per year will be enrolled in the protocol and the accrual will be completed within 5 years. An evaluable patient is defined as one who completes a single fractions of preoperative SRS followed by surgical resection of appropriate brain metastases. Patients who are not evaluable will be replaced.

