4.4 Inclusion criteria

Each subject must meet all of the following inclusion criteria to be enrolled in the study:

- a. Male or female patients \geq 18 years of age
- b. A life expectancy of at least 12 weeks with a Karnofsky performance status of at least 50 (Appendix I)
- c. Patient has no contraindications to MRI scanning with intravenous contrast.
- d. MRI scan consistent with brain metastasis as per radiology report.
- e. The target lesion must measure at least 15 mm in at least one dimension, and no more than 4 cm in any dimension.
- f. Patients must have an extra-cranial primary tumor diagnosis.
- g. Patients will have no more than 4 distinct lesions within the brain. At least 1 lesion has been recommended for surgical removal based on size, symptomology, or regional mass effect on the brain.
- h. The additional lesions will each be treated with stereotactic radiosurgery.
- i. Patients with a documented symptomatic lesion size smaller than 3cm requiring clinical surgical resection
- j. Must be aware of the neoplastic nature of his/her disease and willingly provide written, informed consent after being informed of the procedure to be followed, the experimental nature of the therapy, alternatives, potential benefits, side-effects, risks and discomforts.
- k. Signed consent

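### The primary endpoint compares later tumor volume with the pre-SRS volume of a lesion that is then resected, and no criterion for local failure on MRI is defined

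*Combined protocol and SAP*

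**What the plan says.** Section 2.1 names local control rate as the primary outcome and explains it as "that is, the tumor volume as measured at a later date and compared to the tumor volume at the start of radiotherapy". The protocol summary, under efficacy data, repeats the measure: "Objective local control rate measuring tumor volume". Neither place gives a threshold or a failure event.

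The treatment sequence is in section 3.5: "stereotactic radiosurgery will take place, 1-7 days later, there will be a surgical removal of the tumor". Section 3.7 adds "Only the symptomatic tumor will be removed surgically". Sections 4.2.2 and 7.2 make resection a condition of being analyzed: "An evaluable patient is defined as one who completes a single fractions of preoperative SRS followed by surgical resection of appropriate brain metastases".

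Section 7.4.1 analyzes local control at 6, 12 and 24 months by Kaplan-Meier. The background in section 1.3 uses the same kind of measure; the earlier pre-operative SRS series it cites "demonstrated actuarial LC of 97.7%, 84.6%, and 64.0% at six, twelve, and twenty four months, respectively".

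Section 6.4 refers to RECIST under a heading about CT. Sections 6.2 and 8.2 (item 4) end participation for worsening disease, and for progression or treatment effect at the target that needs repeat surgery or SRS.

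**The concern.** The hypothesis in section 1.3 is that irradiating before surgery lowers recurrence where the tumor was removed. A later volume set against the volume before radiotherapy does not measure that. Once the lesion is out, volume at the site falls because of the surgery, and a recurrence starts from a cavity, not from the original tumor.

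A Kaplan-Meier curve also needs a rule for what counts as failure, when it is dated and who is censored. Without a written rule, these choices can be made after the scans have been seen, in an uncontrolled study of 24 patients. The treatment of withdrawals matters most: if patients who leave because the target site progressed are censored, the failures being counted drop out of the estimate and local control is biased upward.

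**Working it through.** **1. The plan's own figure.** Inputs from section 7.2: control of 60% to be excluded, 85% postulated, one-sided 0.05, 80% power, 20% attrition. One-sample proportion with null variance under the null hypothesis:

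n = [(1.645·√(0.60·0.40) + 0.842·√(0.85·0.15)) / 0.25]² = 19.58, so 20; 20 × 1.2 = 24.

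The stated 24 reproduces. The problem is the definition of the endpoint, not this arithmetic.

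**2. The sequence, side by side.**

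- Reference measurement: tumor volume at the start of radiotherapy (2.1).
- 1-7 days later: the target is removed (3.5, 3.7).
- Analysis population: only patients who had both SRS and resection (4.2.2, 7.2).
- Follow-up MRI: 3, 6, 9 and 12 months, then four-monthly to 3 years, so 16, 20, 24 months and on (5.3, 6.3, 6.5).
- Analysis times: 6, 12 and 24 months (7.4.1), each of which falls on a scheduled MRI.

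In every evaluable patient, surgery lies between the reference volume and every follow-up volume. Scan dates exist. What is missing is the rule that reads a scan as failure or control.

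**3. Whether another section supplies the rule.**

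- Section 6.4 (RECIST): headed CT, although CT appears in section 6.3 only before treatment, for planning. It is not linked to local control, and it conflicts with the volume rule in 2.1.
- Section 8.2, item 4: a withdrawal criterion. It joins tumor progression with treatment effect and applies only when repeat surgery or SRS is needed.
- Section 6.2: ends participation when disease worsens, at any site.
- Neither 6.2 nor 8.2 says whether leaving the study is an event or censoring.
- By contrast, distant failure in section 2.3 does have an observable event, new metastases on MRI.

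**4. Illustration of the literal rule.** Assumptions not in the documents: failure means volume above baseline, and lesions are spheres, V = πd³/6. A 20 mm baseline meets both size limits in section 4.4 (items e and i), so the difference between those limits does not matter here.

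- 20 mm: 4.189 cc; 10 mm: 0.524 cc.
- Ratio: (10/20)³ = 12.5%. The recurrence scores as controlled.

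The effect is not uniform. For an eligible 15 × 10 × 10 mm ellipsoid (0.785 cc), a 10 mm spherical recurrence is 66.7% of baseline and scores as controlled. A 15 mm one (1.767 cc) is 225% and scores as failure.

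**5. How much scoring matters at this sample size.** As simple proportions, (0.85 − 0.60) × 24 = 6 patients separate the two rates, and one patient is 1/24 = 4.2 points. These figures do not carry over directly to a Kaplan-Meier estimate.

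As a what-if, assume success at 19 or more of 24 (exact alpha 0.040), true control of 60%, and a fraction f of true failures read as controlled. Apparent control is then 0.60 + 0.40f. The chance of declaring success is 0.040 at f = 0, 0.087 at f = 0.10, 0.229 at f = 0.25 and 0.656 at f = 0.50. The documents give neither f nor this decision rule.

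**The case against.** The best defense is that everyone knows what is meant. Section 1.3 cites actuarial local control and section 7.4.1 plans Kaplan-Meier, so time to local failure was probably intended. Section 2.1 offers a natural time origin, the start of radiotherapy. The lesion is implied by the objective (patients awaiting resection) and by the target lesion in sections 4.1 and 4.4. RECIST is cited as the response framework, and only its heading says CT.

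Much of this stands. A reader might infer that no local-failure event could be dated at all; the MRI schedule and the plausible origin do not support that. Nor is the lesion left wholly open, although up to 4 lesions are allowed, the unresected ones receive SRS, and 2.1 does not say how they enter. A volume comparison could work for those lesions, but they are not what the primary objective is about.

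The defense does not rescue the rule as written. The probable intention differs from the stated measure, and no section says which governs. RECIST neither refers to local control nor agrees with the volume comparison.

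**Conclusion.** The point holds and must be fixed. Section 2.1 states a measure that is unsuited to a resected target lesion, and the plan gives no criterion for local failure on MRI. This is a wrong rule, not only a missing detail, because following it mainly measures surgery.

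Its effect on the result cannot be sized from the documents. The 12.5% example rests on an assumed failure rule and spherical lesions. A reader might infer that the plan is known to favor pre-operative SRS. The documents do not support that: scoring failure as volume above baseline, or censoring at progression, would usually raise apparent control, but scoring treatment effect under section 8.2 (item 4) as failure would lower it. The documents do not settle which reading applies.

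**What to change.** In section 2.1 and the summary, replace the volume comparison with time from start of SRS to local failure of the operated target lesion.

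- **Event:** new or enlarging contrast-enhancing tumor in or at the margin of the resection cavity, on any follow-up MRI, scheduled or not. Date it at the first MRI that shows it.
- **Reference:** the earliest available post-operative MRI. Section 3.8 mentions MRI beside the 10-14 day visit, while the table in section 6.3 shows none then; these must be reconciled.
- **Criteria:** align section 6.4 with MRI and with this definition, and pre-specify there the threshold for enlarging.
- **Withdrawal:** count tumor progression at the operated site as an event even when it leads to withdrawal under section 6.2 or 8.2. State how withdrawal for distant or systemic worsening is handled.
- **Treatment effect:** record it separately from tumor progression. Give a sensitivity analysis for unresolved cases, including enhancement first seen at 3 months.
- **Death without local failure:** state the handling, for example as a competing event, or censored with a sensitivity analysis.
- **Unresected SRS-treated lesions:** report separately.

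These are changes to wording and scoring that use MRIs already planned. The price is that the observed control rate may be lower than under the current text. If no earlier post-operative MRI exists, residual and recurrent tumor may be hard to separate at 3 months.

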3.0 INVESTIGATIONAL PLAN

3.1 Overall design and plan of the study

Detailed visit-by-visit study procedures and a study flow chart are provided in Section 6.3. Prior to enrollment, all subjects will be evaluated with physical examination, histologic confirmation and baseline imaging to establish the size and location of the brain metastatic lesions. Patients will receive a single SRS radiation dose and then followed periodically for up until 3 years.

3.2 Screening procedures

- Complete physical evaluation with a performance status, vital signs, height, and weight, and a complete medical history.
- CT (computed tomography) Scan of the brain
- MRI (Magnetic Resonance Imaging) Scan of the brain
- For women of childbearing potential, i.e., females who are not at least 1 year postmenopausal or who have not undergone a surgical sterilization procedure, a urine pregnancy test will be done. If this comes back positive or questionable, a serum pregnancy test will be completed by taking a small sample (about 1 teaspoonful) of blood. Pregnant women, or women who are currently breast-feeding an infant, will not be allowed to take part in this study.

3.3 Personnel performing the procedures

All procedures will be performed by appropriate certified medical personnel, including but not limited to physicians, nurses, technologists and research staff. Potential candidates for the study will be identified by [name] based on his clinical judgment of a need for resection of a presumed brain metastasis. Potential research subjects will be sent to radiation oncology co-investigators for possible enrollment, and pre-operative SRS.

